#### 5.2.2 Recording of Adverse Events

Full details of AEs including the nature of the event, start and stop dates, severity (CTCAE grade), seriousness and causality (relationship of the AE to the trial intervention) and outcome will be recorded in the patient's medical records. AEs must be reported from consent and followed until resolution, or for at least 30 days after the last protocol related procedure is performed, whichever comes first or until toxicity has resolved to baseline or  $\leq$  grade 1, or until the toxicity is considered to be irreversible. Perceived lack of efficacy is not an AE.

An exacerbation of a pre-existing condition is an AE. The Investigator does not need to actively monitor patients for AEs once the trial has ended.

#### 5.2.3 Assessment of Adverse Events

All AEs and must be coded and graded according to the NCI Common Terminology Criteria for Adverse Events (NCI-CTCAE) Version 4.03. These criteria can be accessed via the National Cancer Institute Website.

The assessment of AEs is the responsibility of the Investigator (or designee). In determining whether an AE is related to trial participation, Investigators must consider if there is a reasonable possibility of establishing a causal relationship between the event and the protocol related procedures based on their analysis of all the available evidence. The assessment must be made on the basis of anticipated effects of the protocol related procedures as specified below, or related to the patient's disease, either the disease under investigation or a concurrent illness.

The investigator must, whenever possible, provide a causality assessment for AEs based on the information available at reporting and their knowledge of the disease and the trial procedures. The CI shall not downgrade the causality assessment provided by an Investigator.

Although Investigators must record all AEs in the patient notes they are only required to record AEs on the eCRF for the following events if they are a result of a tumour biopsy (percutaneous or endoscopic) or other protocol related procedure:

- Post procedure pain not controlled with simple analgesia
- Pancreatitis
- Post procedure haemorrhage
- Wound infection
- Perforation
- Pneumothorax
- Anaphylactic reaction to local anaesthetic or sedation agents
- Death following complications from biopsy procedure

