	Possible	There is some evidence to suggest a causal relationship (e, g. the event occurs within a reasonable time after administration of the trial treatment/intervention). However the influence of other factors may have contributed to the event (e.g. the patient's clinical condition, other concomitant treatments).
	Probable	There is evidence to suggest a causal relationship and the influence of other factors in unlikely.
	Definitely	There is clear evidence to suggest a causal relationship and other possible contributing factors can be ruled out.
Serious Related and Unexpected	A serious, related and unexpected Event (SRUE) is any	
Events (SRUE)	serious and related event, which is unexpected.	
	Unexpected is any event that is not listed in the protocol as	
	an expected event.	

N.B: To avoid confusion or misunderstanding of the difference between the terms "serious" and "severe", the following note of clarification is provided: "Severe" is often used to describe intensity of a specific event (for example CTCAE grade), which may be of relatively minor medical significance. "Seriousness" is the regulatory definition supplied above.

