## 5.2.4 Reporting of a Serious Adverse Event

Events are only required to be reported as SAEs if they are a result of a tumour biopsy (percutaneous or endoscopic) or other protocol related procedure and meet the regulatory

definition of serious (see section 5.1 Definitions). Investigators must report all SAEs by completing and submitting a SAE report form to the Pharmacovigilance Office, CRUK CTU. SAE reports must be submitted immediately and under no circumstances should this exceed 24 hours following first awareness of the event by the Investigator or site staff.

Pharmacovigilance Office, CRUK CTU, Glasgow

[contact] [contact]

[contact][name]

Email: [contact]

The purpose of this obligation is to ensure the CI on behalf of the Sponsor, has the necessary information to continuously assess the benefit-risk balance of the clinical trial.

For guidance on submitting and completing the initial and follow up SAE forms please refer to the SAE Completion Guidelines, which will be provided by the Pharmacovigilance Office, CRUK CTU, Glasgow. The CI will receive notification, by email, of all SAEs received. SAEs must be reported locally by the PI at each site in accordance with the local practice at their site (e.g. R&D Office).

A follow-up report must be submitted when the SAE resolves, is unlikely to change, or when additional information becomes available. If the SAE meets the criteria for expedited reporting to the REC, then follow up information must be provided as quickly as possible and in the timeframe requested by the CRUK CTU and CI. All follow-up information is required to be reported promptly and follow up reports must be submitted until all AEs listed on the initial SAE report resolve or will never resolve. A follow up report should also be submitted if additional AEs occur or new information becomes available about previously reported AEs.

SAEs are required to be reported from consent for up to 30 days after the end of the final protocol related procedure. Any event that meets the criteria of a SAE (including events that the Investigator thinks are medically important but maybe do not require hospitalisation or are fatal etc.) that occur after 30 days post procedure are also required to be reported if the Investigator thinks that the SAE is related to a trial procedure. The Investigator must report such SAEs to the CRUK CTU Pharmacovigilance Office again without undue delay

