#### 5.3 **Expected Events**

The following is a list of events that are expected as a result of the trial intervention.

- Pain
- Bleeding
- Infection at biopsy site
- Bruising
- Sore throat
- Pancreatitis
- Perforated viscus
- Pneumothorax

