#### 5.4.1 Expedited Reports

CRUK CTU on behalf of the (co) Sponsor is responsible for the expedited reporting of all serious, related and unexpected events to the REC, Sponsor and PIs and trial sites. The CI (or CI designee) is responsible for deciding if an event is unexpected and requires expedited reporting. The requirement for expedited reporting starts with the first REC approval of the trial. It ends with the completion of the trial for all patients recruited.

SAEs will be reported to the REC where in the opinion of the CI the event was:

- Related that is, it resulted from administration of any of the research procedures and is
- Unexpected—that is, the type of event is not listed in the protocol as an expected event.

Reports of related and unexpected SAEs will be generated from the trial database and signed by the CI. The report will then be submitted within 15 days of the CRUK Clinical Trials Unit, Glasgow becoming aware of the event, using the 'Report of Serious Adverse Event form' for non-CTIMPs published by the HRA. If the assessment of causality provided by the investigator differs from that of the CI (assessment is made on behalf of the sponsor), the opinion of both the investigator and CI will be provided in the expedited report.

Master Protocol; v2; 6th October 2017

Investigators will receive all expedited reports. The CI will assess if the risk-benefit assessment has been affected by each serious, related and unexpected event they identify. If the risk-benefit of participation is adversely affected, appropriate prompt action will be decided upon by the CI, Sponsor and Trial Steering Group and implemented by the Trial Management Group.

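### One mandatory sentence in Protocol 5.2.3 ties relatedness to anticipated effects, contradicting the protocol's own separate tests of relatedness and expectedness and risking under-reporting of unlisted biopsy complications

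*Protocol*

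**What the plan says.** Section 5.2.3 sets out the relatedness judgement in three steps.

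- It opens broadly: "Investigators must consider if there is a reasonable possibility of establishing a causal relationship between the event and the protocol related procedures", and they are to do so "based on their analysis of all the available evidence".
- The next sentence narrows this: "The assessment must be made on the basis of anticipated effects of the protocol related procedures as specified below". The only alternative it offers is the patient's disease, meaning the cancer or a concurrent illness.
- The following paragraph asks for a causality assessment "based on the information available at reporting and their knowledge of the disease and the trial procedures", with no reference to a list.

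Elsewhere the two judgements are kept apart. Section 5.1 grades relatedness as possible, probable or definite. The lowest of these grades requires only that "There is some evidence to suggest a causal relationship", with timing given as an example. Section 5.1 defines unexpectedness separately, by absence from the protocol's list. Section 5.4.1 requires both properties for an expedited report: the event resulted from a research procedure, and "the type of event is not listed in the protocol as an expected event". Section 5.2.4 sets follow-up for serious related events of either kind, expected or unexpected.

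Section 5.2.4 also fixes what reaches the trials unit: "Events are only required to be reported as SAEs if they are a result of a tumour biopsy (percutaneous or endoscopic" procedures), or of another protocol procedure, and meet the definition of serious.

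**The concern.** Relatedness asks whether the procedure caused the event. Expectedness asks whether that kind of event was foreseen. Expedited reporting needs events that are related and unforeseen, so the first question cannot be answered by consulting a list of foreseen effects. The narrowing sentence in 5.2.3 does that in mandatory terms.

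The sentence acts at the point that controls reporting. Under 5.2.4 the site's causality call decides whether an SAE form is required, and the CI is notified of the SAEs that are received. The rule in 5.2.3 that the CI may not downgrade an investigator's causality assessment does not help with an event that the site has already attributed to disease. Such an event is recorded in the patient notes, but no SAE form is required. In patients with pancreatic cancer, the disease is a readily available alternative explanation.

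At stake are the expedited route for new risks and the secondary objective in 2.2 on the safety of obtaining biopsies.

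**Working it through.** No sample size, power or rate is involved, and the protocol states no figure to reproduce. The check sets the passages side by side and then matches the two event lists.

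**Step 1. The basis for relatedness in each place**

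| Place | Basis for calling an event related | Depends on a list? |
|---|---|---|
| 5.1, relatedness grades | Evidence of causation, including timing and other factors | No |
| 5.2.3, opening sentence | Reasonable causal possibility, all evidence | No |
| 5.2.3, next sentence | Anticipated effects, or the patient's disease | Yes, list not identified |
| 5.2.3, following paragraph | Information at reporting, knowledge of disease and procedures | No |
| 5.2.4, follow-up of related SAEs | Covers related events whether or not expected | No |
| 5.4.1, expedited reports | Resulted from a research procedure | No (the list enters only in the separate unexpected test) |

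One row stands against the other five. The protocol does not say which prevails.

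**Step 2. Which list is meant**

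The sentence points forward without naming its target. Two lists follow it. The one in 5.2.3 is introduced as the events to be recorded on the eCRF. The one in 5.3 is introduced with "The following is a list of events that are expected as a result of the trial intervention". Either could be intended.

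**Step 3. Matching the lists**

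| 5.2.3 (8 items) | 5.3 (8 items) |
|---|---|
| Pain not controlled by simple analgesia | Pain |
| Pancreatitis | Pancreatitis |
| Haemorrhage | Bleeding |
| Wound infection | Biopsy-site infection |
| Perforation | Perforated viscus |
| Pneumothorax | Pneumothorax |
| Anaphylactic reaction | none |
| Death following biopsy complications | none |
| none | Bruising |
| none | Sore throat |

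Matched: 6. Only in 5.2.3: 8 − 6 = 2. Only in 5.3: 8 − 6 = 2.

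**Step 4. What the strictest reading would leave**

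Suppose a site treated the narrowing sentence as exclusive.

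- If it refers to the 5.2.3 list, the types that are both anticipated and absent from 5.3 number 2 of 8: anaphylactic reaction, and death following biopsy complications.
- If it refers to the 5.3 list, every anticipated type is by definition expected, so the number is 0.

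Two things soften both counts. Section 5.4 asks the CI, when deciding on unexpectedness, to weigh whether an event adds significant information on the specificity, frequency or severity of a known event, so a listed type may still be treated as unexpected. The death item is also not confined to the complications listed beside it.

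**Step 5. Consequence for reporting**

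Under 5.1, 5.2.4 and 5.4.1, a serious unlisted complication judged possibly, probably or definitely related is reportable and can qualify for expedited reporting. Under the literal narrowing sentence, the same event could be attributed to disease and no SAE form would be required. Two sites following the same protocol could therefore handle the same event differently.

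**The case against.** The strongest reply is that the surrounding text already gives the right rule. The sentences on either side of the narrowing one call for a judgement on evidence and knowledge. Sections 5.1 and 5.4.1 define relatedness without a list, and 5.2.4 names no event types when it requires SAE reports. The narrowing sentence does not say that only anticipated effects count, and nothing in the protocol makes disease the default attribution for an unlisted event. How sites would act on the sentence is an inference.

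This stands against the stronger reading. A reader might infer that an unlisted complication cannot be classed as related, that it has no route to an SAE form or the ethics committee, or that the serious, related and unexpected category is almost empty by construction. The documents do not support any of these, because several passages let such an event be graded as related and reported. The count of 2 types is not a firm limit either: it depends on which list is meant, and 5.4 allows listed events to be weighed as unexpected.

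Two further points are fair. The SAE completion guidelines are not shown and may already deal with this. The separate rule in 5.2.3 that limits eCRF recording to listed events also narrows the complication profile, and it would do so whatever happened to this sentence.

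The reply does not remove the contradiction. The protocol gives no order of precedence, and the narrowing sentence is mandatory and sits at the step that controls SAE reporting.

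**Conclusion.** The point holds as an internal contradiction with a plausible effect on safety reporting. One mandatory sentence in 5.2.3 mixes expectedness into causality, refers to an unidentified list, and conflicts with its own paragraph and with 5.1, 5.2.4 and 5.4.1. A site that followed it literally could leave a serious unlisted biopsy complication unreported, which would weaken expedited reporting and the biopsy-safety objective.

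The size of the effect cannot be given as a number of events. Section 3.1 plans 2,500 to 5,000 patients, but the protocol gives no rate of unlisted serious complications, so that range describes only the population to which the wording applies. The list counts in the working (2 of 8, or 0) describe the strictest reading and assume that the sentence is treated as exclusive. Under the rest of the protocol the category remains open.

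The sentence should be corrected, because the change is small and it affects the detection of new risks.

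**What to change.** Replace the narrowing sentence in 5.2.3, including its clause on disease, with: *Relatedness is judged on all available evidence using the categories in 5.1, whether or not the event is listed in 5.2.3 or 5.3; expectedness is then assessed separately against 5.3.* Check the SAE completion guidelines and align them if they do not already say this.

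The cost is one protocol sentence, submitted through the amendment route in 10.7, and probably a few more SAE forms for unlisted events. No trial procedure changes. The change leaves the rule limiting eCRF recording to listed events as it is, so non-serious unlisted complications would still not have to be entered there.

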## 5.2.4 Reporting of a Serious Adverse Event

Events are only required to be reported as SAEs if they are a result of a tumour biopsy (percutaneous or endoscopic) or other protocol related procedure and meet the regulatory

definition of serious (see section 5.1 Definitions). Investigators must report all SAEs by completing and submitting a SAE report form to the Pharmacovigilance Office, CRUK CTU. SAE reports must be submitted immediately and under no circumstances should this exceed 24 hours following first awareness of the event by the Investigator or site staff.

Pharmacovigilance Office, CRUK CTU, Glasgow

[contact] [contact]

[contact][name]

Email: [contact]

The purpose of this obligation is to ensure the CI on behalf of the Sponsor, has the necessary information to continuously assess the benefit-risk balance of the clinical trial.

For guidance on submitting and completing the initial and follow up SAE forms please refer to the SAE Completion Guidelines, which will be provided by the Pharmacovigilance Office, CRUK CTU, Glasgow. The CI will receive notification, by email, of all SAEs received. SAEs must be reported locally by the PI at each site in accordance with the local practice at their site (e.g. R&D Office).

A follow-up report must be submitted when the SAE resolves, is unlikely to change, or when additional information becomes available. If the SAE meets the criteria for expedited reporting to the REC, then follow up information must be provided as quickly as possible and in the timeframe requested by the CRUK CTU and CI. All follow-up information is required to be reported promptly and follow up reports must be submitted until all AEs listed on the initial SAE report resolve or will never resolve. A follow up report should also be submitted if additional AEs occur or new information becomes available about previously reported AEs.

SAEs are required to be reported from consent for up to 30 days after the end of the final protocol related procedure. Any event that meets the criteria of a SAE (including events that the Investigator thinks are medically important but maybe do not require hospitalisation or are fatal etc.) that occur after 30 days post procedure are also required to be reported if the Investigator thinks that the SAE is related to a trial procedure. The Investigator must report such SAEs to the CRUK CTU Pharmacovigilance Office again without undue delay

Serious and related events, whether they are expected or not, must be followed up for at least 30 days or longer in the case of pancreatitis by providing follow-up SAE reports until the reaction has completely resolved or will never resolve.

For any questions relating to SAE reporting, please contact the Pharmacovigilance team:

Pharmacovigilance Office, CRUK CTU, Glasgow

Email: [contact]

Master Protocol; v2; 6th October 2017

[contact]

Contact details are also provided at the front of the protocol and in the SAE completion guidelines.

#### 5.3 **Expected Events**

The following is a list of events that are expected as a result of the trial intervention.

- Pain
- Bleeding
- Infection at biopsy site
- Bruising
- Sore throat
- Pancreatitis
- Perforated viscus
- Pneumothorax

#### 5.4 Identifying Events for Expedited Reporting

The assessment of SAEs for expedited reporting will be undertaken by the CTU and CI based on the list of expected events noted above. When deciding if an event is unexpected, the CI should whether the event adds significant information on the specificity, increase of occurrence or severity of a known, serious and related event that is already recognised and documented in the protocol.

#### 5.4.1 Expedited Reports

CRUK CTU on behalf of the (co) Sponsor is responsible for the expedited reporting of all serious, related and unexpected events to the REC, Sponsor and PIs and trial sites. The CI (or CI designee) is responsible for deciding if an event is unexpected and requires expedited reporting. The requirement for expedited reporting starts with the first REC approval of the trial. It ends with the completion of the trial for all patients recruited.

SAEs will be reported to the REC where in the opinion of the CI the event was:

- Related that is, it resulted from administration of any of the research procedures and is
- Unexpected—that is, the type of event is not listed in the protocol as an expected event.

Reports of related and unexpected SAEs will be generated from the trial database and signed by the CI. The report will then be submitted within 15 days of the CRUK Clinical Trials Unit, Glasgow becoming aware of the event, using the 'Report of Serious Adverse Event form' for non-CTIMPs published by the HRA. If the assessment of causality provided by the investigator differs from that of the CI (assessment is made on behalf of the sponsor), the opinion of both the investigator and CI will be provided in the expedited report.

Master Protocol; v2; 6th October 2017

Investigators will receive all expedited reports. The CI will assess if the risk-benefit assessment has been affected by each serious, related and unexpected event they identify. If the risk-benefit of participation is adversely affected, appropriate prompt action will be decided upon by the CI, Sponsor and Trial Steering Group and implemented by the Trial Management Group.

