# Related Adverse Event (RAE) A related adverse event (RAE) is any untoward and unintended occurrence in a subject administered trial treatment/intervention which is thought to be caused by or related to the trial treatment/intervention. **Serious Adverse Event (SAE)** A serious adverse event (SAE) means any untoward medical occurrence that at any dose requires the following, whether or not considered related to the trial treatment. Requires inpatient hospitalisation or prolongation of existing hospitalisation\* Results in persistent or significant disability or incapacity Results in a congenital anomaly/birth defect Is life-threatening (i.e. at the time of the event)\*\* Or results in death Is considered medically significant by the Investigator\*\*\* \*Requires in-patient hospitalisation should be defined as a hospital admission required for treatment of an AE. No time frame is specified for the duration of the admission. \*\*Life threatening means that the patient was at immediate risk of death from the event as it occurred. It does not include an event that, had it occurred in a more serious form, might have caused death. \*\*\*Considered medically significant by the Investigator are events that may not result in death, are not life threatening, or do not require hospitalisation, but may be considered a serious adverse experience when, based upon appropriate medical judgement, the event may jeopardise the patient and may require medical or surgical intervention to prevent one of the outcomes listed above. Medical and scientific judgement should be exercised in deciding whether an event is "serious" in accordance with this criterion. Serious and Related Adverse Event A serious and related adverse event (SRAE) is a SAE that (SRAE) may be related to trial treatment/intervention. The assessment of "relatedness" is primarily the responsibility of the Principal Investigator (PI) at site or agreed designee. SAEs will be considered related if the SAE is documented as possibly, probably or definitely related to protocol

Master Protocol; v2; 6th October 2017 IRAS: 184216

treatment. The assessment of relatedness is made using

	the following:	
	Relationship	Description
	Unrelated	There is no evidence of any causal relationship.

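### The REC reporting trigger in section 5.4.1 rests relatedness on the CI's opinion, which conflicts with sections 5.1 and 5.2.3 when the site calls an unlisted SAE related and the CI does not

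*Protocol*

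**What the plan says.** Four places in Protocol section 5 bear on whose causality assessment counts.

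- **Section 5.1, entry for serious and related adverse events.** The assessment of relatedness "is primarily the responsibility of the Principal Investigator (PI) at site or agreed designee". The threshold is low: "SAEs will be considered related if the SAE is documented as possibly, probably or definitely related to protocol" treatment. An event that is serious, related and not listed as expected is then a serious, related and unexpected event (SRUE).
- **Section 5.2.3.** "The CI shall not downgrade the causality assessment provided by an Investigator".
- **Section 5.4.1, opening.** The CTU is "responsible for the expedited reporting of all serious, related and unexpected events to the REC, Sponsor and PIs and trial sites". The CI's part is described next: "The CI (or CI designee) is responsible for deciding if an event is unexpected and requires expedited reporting".
- **Section 5.4.1, trigger and what follows.** "SAEs will be reported to the REC where in the opinion of the CI the event was" related and unexpected. The next paragraph adds that where the investigator's causality differs from the CI's, "the opinion of both the investigator and CI will be provided in the expedited report".

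Section 5.2.4 governs what reaches the CI: sites submit SAEs that result from a biopsy or other protocol procedure within 24 hours, and "The CI will receive notification, by email, of all SAEs received".

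**The concern.** Sections 5.1 and 5.2.3 protect the site's attribution. The trigger sentence in 5.4.1 then applies a relatedness test that depends on the CI's opinion. If the CI disagrees with a site that has called an unlisted serious event related, the trigger gives the result that the no-downgrade rule appears meant to prevent: the CI's view prevails and no expedited report is generated.

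What is at stake is prompt notice. The expedited report is due within 15 days of the CTU becoming aware and goes to the REC, the Sponsor, and the PIs and sites. Biopsy safety is a secondary objective (section 2.2), and section 3.1 plans for 2,500 to 5,000 patients. An unlisted biopsy complication that one site suspects is the kind of signal other sites would want early.

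**Working it through.** No arithmetic applies. The protocol gives no figure on this point, neither a rate of serious unlisted events nor a rate of disagreement between site and CI. The check sets the provisions side by side.

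**Step 1: hold the other conditions fixed.** Take an event that is serious, has been submitted under 5.2.4 and is not on the section 5.3 list. Listed events (among them pain, bleeding, biopsy-site infection, pancreatitis, perforated viscus and pneumothorax) are generally not expedited whoever judges causality, so they drop out.

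**Step 2: go through the four combinations of site and CI opinion.**

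| Site | CI | SRUE under 5.1 and 5.2.3? | 5.4.1 trigger met, read literally? |
|---|---|---|---|
| Related | Related | Yes | Yes |
| Unrelated | Related | Not on the site's assessment; nothing stops the CI upgrading | Yes, with both opinions given |
| Related | Unrelated | Yes: the site's rating may not be downgraded | No |
| Unrelated | Unrelated | No | No |

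Only the third row gives opposite answers.

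**Step 3: ask whether another provision settles the third row.**

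- The opening duty in 5.4.1 covers all SRUEs. With the 5.1 definition this points to a report.
- The sentence on the CI's role names unexpectedness and the need for expedited reporting. It does not name causality, but the second element leaves the CI room to decide that no report is needed.
- The both-opinions sentence foresees a difference in causality. It governs the content of a report and does not state when one is made. If it is taken to presuppose a report in the third row, it contradicts the trigger sentence shortly before it. If it is not, the third row goes unreported to the REC on an expedited basis.

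On either reading the passages need reconciling.

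**Step 4: check how far the third row matters in practice.** Under 5.2.4 sites need submit SAEs only when they result from a biopsy or other protocol procedure. Most SAEs that the CI sees will therefore already carry a site attribution, and the usual form of disagreement will be the third row. The second row can arise only for an event the site was not obliged to submit.

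**Step 5: trace what still happens to a third-row event.** It reaches the CTU Pharmacovigilance Office within 24 hours, the CI is notified by email, and the PI reports it locally (5.2.4). It may appear in the annual progress report to the REC (5.5), which covers unexpected events resulting from participation but is not prompt. What could be missed is the expedited notice to the REC, other PIs and sites.

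**The case against.** The strongest reply is that the section, read as a whole, shows that a report is intended. The opening duty covers all SRUEs, 5.1 defines relatedness mainly through the PI, 5.2.3 bars downgrading, and the both-opinions sentence would have almost no work to do if disagreement of the usual kind stopped the report. Non-reporting follows only if one lead-in is read alone and placed above the rest.

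Much of this stands. It is good evidence of intent, and the CTU may well operate that way. It does not remove the conflict, because the lead-in is the one sentence that states the conditions for a REC report, and it names the CI's opinion for both of them. The protocol also plainly allows the CI a causality opinion that differs from the site's, so 5.2.3 alone does not make the third combination impossible.

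A reader might be tempted by stronger readings that the document does not support:

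- That such an SAE goes unreported altogether. It still reaches the CTU, the CI and the local R&D route under 5.2.4.
- That any site-attributed biopsy SAE is affected. Only events outside the 5.3 list are.
- That the expedited report is the only route to a risk-benefit review. Section 5.2.4 says SAE submission itself exists so that the CI can assess benefit and risk continuously, and 10.8.2 gives the CI SAE review and ongoing risk-benefit oversight.
- That the site's causality is binding, or that the CI's view is the sole criterion. Section 5.1 says primarily, and 5.4.1 does not contain the word only.
- That a number of missed events can be estimated. Any such figure would rest on invented rates.

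**Conclusion.** The concern holds as an internal conflict in the safety-reporting rules. The 5.4.1 lead-in cannot be squared with 5.1, 5.2.3 and the both-opinions sentence for one of the four combinations of site and CI opinion, and only for serious events not listed in 5.3. In that case the literal trigger is not met, and expedited notice to the REC, other PIs and sites could be missed.

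The size cannot be expressed as a count, since the protocol gives neither an event rate nor a disagreement rate. The conclusion rests on two things: that the CI may form a causality opinion different from the site's, which 5.4.1 itself foresees, and that those applying the section may read the lead-in as a condition for reporting. Whether the CTU's working practice already resolves the conflict cannot be seen from the protocol. The point is worth correcting because the disputed combination is likely to be the usual form of disagreement, and the correction is simple.

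**What to change.** Reconcile the passages by rewording the 5.4.1 lead-in along these lines: an SAE will be reported to the REC where it is related, in the opinion of either the investigator or the CI, and unexpected, as assessed by the CI. Keep the sentence that gives both opinions when they differ; under the new lead-in it has a clear role. It would help to add that the CI may raise but not lower the investigator's causality, so that 5.4.1 and 5.2.3 read alike.

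The cost is one sentence in the next amendment, a matching line in the pharmacovigilance instructions, and a few more expedited reports.
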